4.2 INCLUSION CRITERIA

1. Participation and completion in the AP-003-C study
2. Able to provide written informed consent to participate in the study
3. Willing and able to comply with all study requirements and instructions of the site study staff
4. Male or female, 40 years to 85 years old (inclusive), as assessed in the AP-003-C main study
5. Must be ambulatory, as assessed in the AP-003-C main study
6. Study knee must have a clinical diagnosis of OA and supported by radiological evidence (Kellgren Lawrence Grade 4) as assessed in the AP-003-C main study.
7. Moderate to moderately-severe OA pain in the index knee (rating of at least 1.5 on the WOMAC Index 3.1 5-point Likert Pain Subscale), as assessed in the AP-003-C main study
8. Moderate to moderately-severe OA function in the index knee (rating of at least 1.5 on the WOMAC Index 3.1 5-point Likert Function Subscale), as assessed in the AP-003-C main study
9. WOMAC A, 5-point Likert pain subscale <1.5 in the contralateral knee, as assessed in the AP-003-C main study
10. Ability to discontinue NSAID ± 72 hours before/after injections (in-office visits). Low-dose Aspirin (81 mg) is allowed during the study but must not be taken at least 24 hours prior to in-office visits.
11. No analgesia (including acetaminophen [paracetamol]) taken 24 hours prior to an efficacy measure

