6.1.1 WOMAC® Osteoarthritis Index ([Bellamy 1988](#))

WOMAC Index 3.1 should be completed by subjects at each in-clinic visit, pre-dose. All subjects are required to take at least 5 minutes to complete the questionnaire.

Subjects are asked about their pain, stiffness, and function in the study knee (study joint) due to arthritis during the last 24 hours. This will be assessed at every in-office visit.

Subjects will also be asked about their pain, stiffness, and function in the non-study knee. This will be assessed at Enrollment and Visit 17 (or early termination visit).

Subjects respond to each subscale by using a 5-point adjectival Likert score (0 = none, 1 = mild, 2 = moderate, 3 = severe, 4 = extreme).

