6.2.2 Clinical laboratory tests

Subjects will have lab tests at Visit 17 (or Early Termination) to evaluate for changes from Screening (Visit 1) of the Main Study.

The following analysis will be conducted:

Serum biochemistry: Sodium, potassium, chloride, bicarbonate, glucose, urea, creatinine, creatine kinase, urate, phosphate, total calcium, cholesterol, albumin, globulins, protein, total bilirubin, conjugated bilirubin, gamma glutamyltransferase (GGT), alkaline phosphatase (ALP), alanine aminotransferase (ALT), aspartate aminotransferase (AST) and lactate dehydrogenase (LD).

Hematology: Hemoglobin, red blood cell count, hematocrit, mean cell volume (MCV), mean cell hemoglobin (MCH), mean cell hemoglobin concentration (MCHC), platelets, white cell count, neutrophils, lymphocytes, monocytes, eosinophils, and basophils.

TABLE 6.1 SCHEDULE OF ASSESSMENTS AND PROCEDURES

| | Enrollment ¹ | Post-treatment phone contact | Week 12 | Post-treatment phone contact | Week 24 | Post-treatment phone contact | Week 36 | Post-treatment phone contact | Week 40 Final Visit | Early Termination |
|---------------------------------------|-------------------------------------|----------------------------------|------------------------|-----------------------------------|-------------------------|-----------------------------------|-------------------------|-----------------------------------|-------------------------|-------------------------|
| Visit # Day # | 9 ¹ Day -170 to Day 0 | 10 24 hours following Visit 9 | 11 Day 84 ± 14 days | 12 24 hours following Visit 11 | 13 Day 168 ± 14 days | 14 24 hours following Visit 13 | 15 Day 252 ± 14 days | 16 24 hours following Visit 15 | 17 Day 280 ± 14 days | 18 Early Termination |
| Informed Consent | X | | | | | | | | | |
| Inclusion/exclusion criteria | X | | | | | | | | | |
| Medical history/prior medications | X | | | | | | | | | |
| Concomitant medications | X | X | X | X | X | X | X | X | X | |
| Physical examination | X | | X | | X | | X | | X | X |
| Vital Signs | X | | X | | X | | X | | X | X |
| WOMAC ² | X ² | | X | | X | | X | | X ² | X ² |
| Subject's global assessment (PGA) | X | | X | | X | | X | | X | X |
| X-ray | X ³ | | | | | | | | X | X ⁸ |
| Clinical laboratory tests | | | | | | | | | X | X |
| Urine Analysis ⁴ | X ⁴ | | | | | | | | | |
| Treatment with study drug | X | | X | | X | | X | | | |
| Rescue medication ⁵ | X ⁵ | | X | | X | | X | | X | X |

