- Change in contralateral knee pain (WOMAC A) between Visit 9 and Visit 17
- Change in contralateral knee stiffness (WOMAC B) between Visit 9 and Visit 17
- Change in contralateral knee function (WOMAC C) between Visit 9 and Visit 17
- Time to Total Knee Replacement (TKR)
- Use of rescue analgesia (amount of acetaminophen used)

Exploratory efficacy analyses include the mean change and percent change in WOMAC A, WOMAC B, WOMAC C, WOMAC A1-2, WOMAC A3-5, PGA and amount of acetaminophen used from Visit 1 to Visit 17 using an analysis of covariance model, adjusted for baseline value.

Percent responders using the OMERACT-OARSI responder criteria will be analyzed defined as the percent of subjects whom respond to treatment from Visit 1 to Visit 17. Interim visits will also be analyzed.

1. High improvement in pain or in function $\geq 50\%$ and absolute change in Likert pain scale of ≥ 1 OR
2. Improvement in at least two of the 3 following:
 - a. pain $\geq 20\%$ and absolute change in Likert score ≥ 0.5
 - b. function $\geq 20\%$ and absolute change in Likert score ≥ 0.5
 - c. subject's global assessment $\geq 20\%$ and absolute change in Likert score ≥ 0.5

All of the above endpoints will be evaluated via descriptive statistics and confidence intervals.

The WOMAC Pain Score, the WOMAC Function Score, then PGA score and the OMERACT-OARSI responder criteria, will be analyzed via a repeated measures analysis of variance to determine if there is a significant time effect for these endpoints. Also, to aid in the interpretation of these results, a stability analysis will be performed on these same endpoints. That is, mean pairwise differences between administration time points will be calculated along with their 95% confidence intervals. If stability is achieved at some time point, then the following mean differences should be not be different from zero, in that the confidence interval should include zero.

Adverse events will be tabulated for both number of subjects and number of events by subject and overall study population, summarized by any event, body system, and preferred term. Summaries by serious, severity, and relationship will also be done.

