4. HYPOTHESES AND METHODS

4.1 Primary Analysis Methodologies

Since this is an observational study on the repeat administration of Ampion 4 mL injection, no formal hypotheses will be tested in this study. There will be no comparisons made to threshold values or to “historical” control values. There is no comparator in this study.

All analyses will be descriptive in nature and will be performed at each efficacy assessment (Visit 9 (Enrollment), Visit 11 (Week 12), Visit 13 (Week 24), Visit 15 (Week 36) and Visit 17 (Week 40)). For dichotomous outcomes, the percentage of patients with that outcome will be estimated and exact 95% binomial confidence intervals will be calculated. These dichotomous outcomes are:

- The incidence of treatment emergent adverse events
- Responder status based on the OMERACT-OARSI responder criteria
- Evaluate OMERACT-OARSI ‘controlled’ responder defined as a 20% improvement in Pain and Function and 0.5 point absolute change in the 5-point Likert Scale
- Evaluate 20% improvement in PGA and 0.5 point absolute change in the 5-point Likert Scale

The outcomes with more continuous responses will be analyzed via descriptive statistics (n, mean, standard deviation, median, minimum, and maximum). Also, 95% confidence intervals from the mean response will be calculated. These outcomes are:

- Mean change and percent change in WOMAC A pain subscore
- Mean change and percent change in WOMAC B stiffness subscore
- Mean change and percent change in WOMAC C physical function subscore
- Mean change and percent change in PGA
- Mean Change and percent change in WOMAC A pain subscore questions 1 and 2 (pain with movement)
- Mean Change and percent change in WOMAC A pain subscore questions 3–5 (resting pain)
- Change in contralateral knee pain (WOMAC A)
- Change in contralateral knee stiffness (WOMAC B)
- Change in contralateral knee function (WOMAC C)

Differences in pain scores between successive visits will be estimated via descriptive statistics and confidence intervals.

The time to total knee replacement will be summarized using Kaplan-Meier methodologies. The use of rescue analgesia will be summarized as the dichotomous outcome on the number of patients using rescue medication and as continuous variables on the number of medications use.

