This is an Open Label Extension study, which is designed to assess the safety of patients who have previously completed the main AP-003-C study. It is also desirable to assess the efficacy of all patients relative to their original baseline and first injection and exposure to the investigational product. Thus, the previously mentioned statistics will be calculated using the baseline from the main study, AP-003-C.

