4.2 Definition of Study Visits

This clinical trial has a total of 7 study visits, including telephone contacts, during the 52-week study (see Section 10 of this document for details). The time on study for each subject observation will be defined relative to Day 0/Baseline, the day of the initial dose for this study. For analysis, the Baseline measure is the latest measure prior to initiation of treatment.

	Enrollment	Post Treatment Phone Contact	Week 12	Post Treatment Phone Contact	Week 24	Post Treatment Phone Contact
Visit # Day #	9 Day-170 to 0	10 24 hours post Visit 9	11 Day 84± 14 days	12 24 hours post Visit 11	13 Day 168 ± 14 days	14 24 hours post Visit 13

	Week 36	Post Treatment Phone Contact	Week 40 Final Visit	Early Termination
Visit # Day #	15 Day 252 ± 14 days	16 24 hours post Visit 15	17 Day 280 ± 14 days	18 Early Termination

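### SAP 4.1, read literally, takes contralateral-knee change from the main-study baseline where Protocol 10.4.2 takes it from Visit 9; for pain, that earlier reading may have been capped at entry

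*SAP*

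**What the plan says.** - **SAP 4.1** lists change in contralateral pain, stiffness and function among the continuous outcomes, each to be summarised with a mean and 95% confidence interval. Its last paragraph gives a reason, "It is also desirable to assess the efficacy of all patients relative to their original baseline", and then the rule: "Thus, the previously mentioned statistics will be calculated using the baseline from the main study, AP-003-C".
- **SAP 4.2** places time on study "relative to Day 0/Baseline, the day of the initial dose for this study" and takes as Baseline the latest measure before treatment starts.
- **Protocol 10.4.2** defines the pain endpoint as "Change in contralateral knee pain (WOMAC A) between Visit 9 and Visit 17", with matching definitions for stiffness and function. In the same list, the study-knee WOMAC endpoints do name the main-study Visit 1/Day 0.
- **Protocol 4.2, inclusion 9**, requires "WOMAC A, 5-point Likert pain subscale <1.5 in the contralateral knee, as assessed in the AP-003-C main study". No such limit is set for contralateral stiffness or function.
- **Protocol 6.1.1 and SAP 2.3** place the contralateral WOMAC in this study at Enrollment (Visit 9) and at Visit 17 or early termination only. SAP 3.2 and 4.1 nevertheless list all exploratory endpoints at Visits 9, 11, 13, 15 and 17.
- **SAP section 6** contains a general statement about modifications and no specific change for these endpoints.

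**The concern.** The two documents give different baselines for the same three endpoints, and the two baselines are not interchangeable. The main-study pain reading for this knee was subject to an entry ceiling; the protocol does not re-apply that ceiling at Visit 9. When subjects are kept because a noisy reading is low, their later readings are higher on average even if nothing has changed. A main-study-baseline analysis could therefore report worsening of contralateral pain that comes only from the entry criterion, and the SAP attaches no caveat.

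There is also a question of feasibility. The only main-study contralateral value that either document mentions is the pain score used for entry. If stiffness and function were not recorded for that knee, two of the three endpoints cannot be calculated under the SAP rule.

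**Working it through.** The documents give no contralateral data and no expected change, so there is no plan figure to reproduce. The check has two parts.

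**1. Which baseline applies**

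| Source | Baseline for contralateral change |
|---|---|
| Protocol 10.4.2 | Visit 9 |
| SAP 4.1, last paragraph | Main study, for all listed statistics |
| SAP 4.2 | First dose of this study (Visit 9) |
| SAP section 6 | No change declared |

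The SAP thus disagrees with the protocol and with itself. Because Protocol 10.4.2 names the main-study visit for the study-knee WOMAC endpoints and omits it for the contralateral ones, the Visit 9 definition looks deliberate.

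**2. What the main-study baseline could do to pain**

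Inputs from the documents: cap below 1.5 (Protocol 4.2); items scored 0 to 4 (Protocol 6.1.1); 100 subjects anticipated (SAP 2.4), used only for standard errors.

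Assumed, because the documents give no values: mean contralateral pain before the cap 0.5 to 2.0, SD 0.6 or 0.8, test-retest reliability r 0.6 to 0.8, and no true change.

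If the capped reading Y1 is itself the baseline and Y2 is a later reading:

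E[Y2 − Y1 | Y1 < 1.5] = (1 − r) × SD × φ(a)/Φ(a), with a = (1.5 − mean)/SD.

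Example with mean 1.0, SD 0.8, r 0.7: a = 0.5/0.8 = 0.625; φ(a) = 0.328; Φ(a) = 0.734; ratio 0.447; result 0.3 × 0.8 × 0.447 = +0.107.

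Closed-form results for SD 0.8:

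| Mean before cap | Share below 1.5 | r = 0.8 | r = 0.7 | r = 0.6 |
|---|---|---|---|---|
| 0.5 | 0.89 | +0.033 | +0.049 | +0.065 |
| 1.0 | 0.73 | +0.072 | +0.107 | +0.143 |
| 1.5 | 0.50 | +0.128 | +0.191 | +0.255 |
| 2.0 | 0.27 | +0.197 | +0.296 | +0.395 |

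With SD 0.6 the same grid runs from +0.013 (mean 0.5, r 0.8) to +0.334 (mean 2.0, r 0.6).

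A simulation of 1,000,000 subjects per setting (SD 0.8, scores clipped to 0–4 in steps of 0.2) gave +0.034 to +0.400 from the capped baseline. From Visit 9 to Visit 17 it gave −0.003 to +0.002. When the cap was applied to an earlier reading and the baseline was a separate later one, it gave −0.001 to +0.002.

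**Scale against precision.** In the simulation the standard error of the mean change at 100 subjects was 0.040 to 0.065. At r = 0.7 the artefact is 0.050/0.048 ≈ 1 standard error for mean 0.5, 0.107/0.054 ≈ 2 for mean 1.0, and more for higher means.

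**Stiffness and function.** Neither was capped. With function as the model (true-score correlation with pain 0.8, mean 1.0, SD 0.8, r 0.7), the shift was −0.001 if the measurement errors were independent of the pain error, +0.054 if they correlated 0.5, and +0.086 if they correlated 0.8.

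**Is the capped reading the baseline?** Protocol 6.2.2 describes the later laboratory tests as there "to evaluate for changes from Screening (Visit 1) of the Main Study", so Screening is Visit 1. Protocol 10.3.9 puts the first main-study injection at Visit 1, and Protocol 10.4.2 equates Visit 1 with Day 0. This fits a single reading but does not prove one. The main-study protocol is not among the documents.

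**The case against.** The strongest reply is that the SAP never meant this. The sentence before the rule calls it also desirable to look back to the original baseline, which can be read as an added analysis. Its stated purpose is efficacy since first exposure, which hardly concerns a knee that is not injected. SAP 4.2 keeps a baseline in this study. Protocol 10.3.6 foresees several baselines, and Protocol 10.3.11.5 defines the general efficacy baseline as main-study Day 0. This makes the SAP ambiguous. It does not exempt the contralateral endpoints: the operative sentence is unconditional, and the endpoint-specific definition in Protocol 10.4.2 is clear. Even as an addition, the main-study version would appear without a caveat.

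Second, the size rests wholly on assumptions and may be trivial. That stands.

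Third, Visit 9 may not be entirely free of selection. Eligibility is reviewed there, and exclusion 11 removes subjects whose pain elsewhere in the lower limbs could interfere with assessment of the study knee. That also stands in part: the 0.00 from Visit 9 assumes no such selection on contralateral pain. Exclusion 11 sets no numerical limit, so its effect cannot be calculated.

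A reader might go further and infer that the SAP is bound to show an untreated knee worsening beside a treated knee improving, since the study knee was selected for pain of at least 1.5. The documents do not support that. SAP 4.1 says the study has no comparator, no planned efficacy table in SAP section 7 names the contralateral knee, and neither document calls it an internal reference. Nor is it untreated: Protocol 8.1 gives it standard of care, and exclusion 14a allows hyaluronic acid and steroid injections there, except within 14 days of an Ampion injection.

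**Conclusion.** The baseline conflict is real and can be read directly from the text: SAP 4.1, taken literally, departs from Protocol 10.4.2 for three endpoints without saying so, and is at odds with SAP 4.2.

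The bias is conditional. It applies directly to WOMAC A only, and only if the qualifying reading below 1.5 is also the main-study baseline. In that case the expected spurious rise is about +0.01 to +0.40 points over assumed means of 0.5 to 2.0, SDs of 0.6 to 0.8 and reliabilities of 0.6 to 0.8, against about 0.00 from Visit 9. It is negligible if few knees were near the cap and absent if the baseline was a separate later reading. Stiffness and function would shift only through correlated error, and may not be available at that baseline at all; that last point is inferred from the documents' silence.

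Severity is minor. The endpoints are exploratory and descriptive, no hypothesis is tested on them, and the primary adverse-event endpoint is unaffected.

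**What to change.** 1. In SAP 4.1, exempt the three contralateral endpoints from the main-study-baseline paragraph. Suggested text: *Change in contralateral WOMAC A, B and C is calculated from Visit 9 to Visit 17 (or Early Termination).* This restores the Protocol 10.4.2 definition and uses the early-termination reading already collected under Protocol 6.1.1.
2. If a main-study-baseline version of contralateral WOMAC A is kept, label it supplementary and note that it is subject to regression to the mean from the entry cap of 1.5.
3. In SAP 3.2 and 4.1, limit the visit list for these endpoints to Visit 9 and Visit 17 or Early Termination, consistent with SAP 2.3.

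The cost is a few sentences in the SAP and no new data. The downside is that a one-year contralateral contrast is no longer a main result.

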4.2 Definition of Study Visits

This clinical trial has a total of 7 study visits, including telephone contacts, during the 52-week study (see Section 10 of this document for details). The time on study for each subject observation will be defined relative to Day 0/Baseline, the day of the initial dose for this study. For analysis, the Baseline measure is the latest measure prior to initiation of treatment.

	Enrollment	Post Treatment Phone Contact	Week 12	Post Treatment Phone Contact	Week 24	Post Treatment Phone Contact
Visit # Day #	9 Day-170 to 0	10 24 hours post Visit 9	11 Day 84± 14 days	12 24 hours post Visit 11	13 Day 168 ± 14 days	14 24 hours post Visit 13

	Week 36	Post Treatment Phone Contact	Week 40 Final Visit	Early Termination
Visit # Day #	15 Day 252 ± 14 days	16 24 hours post Visit 15	17 Day 280 ± 14 days	18 Early Termination

4.3 Number of subjects to receive study drug

It is estimated that approximately 160 subjects will receive a single (1) intra-articular injection of 4 mL Ampion. The injections will be given 12 weeks apart for a series of 4 injections.

4.4 Disposition of subjects

Disposition of subjects, including study completion status and response to therapy as measured by WOMAC subscores and PGA, will be summarized by age group, race, and gender for each of the analysis populations.

4.5 Interim analysis

There will be no interim analysis.

4.6 Blinding and randomization

This is an open-label study where all subjects will receive Ampion 4mL as an intra-articular injection in the study knee.

4.7 Data presentation

4.7.1 Demographic and Baseline Characteristics:

Demographic (e.g., age, sex, race, and ethnicity) and Baseline characteristics (e.g., weight, height, prior injection of another intra-articular therapeutic for OA of the knee) will be summarized using descriptive statistics, overall and by treatment group for the ITT analysis population.

4.7.2 Medical History and Physical Examination:

The number and percent of subjects with past and current medical disorders at the time of randomization will be presented overall for the ITT analysis population. Results of any abnormalities documented from the abbreviated physical examination at Baseline and Week 40, will be summarized overall for the safety and ITT analysis populations.

4.7.3 Concomitant Medications or Treatments:

The number and percent of subjects receiving concomitant medications or treatments prior to and during the study and at the final visit will be tabulated and presented overall for the ITT analysis population. Concomitant medications/treatments will be

summarized using descriptive statistics and will be presented by type of drug (WHO DRUG classification) overall for the safety and ITT analysis populations.

4.7.4 Safety data:

Safety data will be evaluated by changes in vital sign measurements, physical exam, laboratory analysis, and the frequency and severity of AEs. Concomitant medication will be recorded for safety.

Adverse events:

The Investigator is responsible for monitoring the safety of subjects who have enrolled in the study. All AEs considered related, or possibly related to Ampion, will be followed until the event resolves or stabilized without further change. Subjects will be followed for the occurrence of AEs until 12 weeks after the first dose of study medication.

Investigators are required to document all AEs occurring during the clinical trial, commencing with the first day of treatment through the end of study. AEs should be properly documented on the appropriate CRF pages.

The severity of AEs (mild, moderate, severe), relatedness (related, possibly related, unrelated) along with the duration, action taken, and outcome (e.g., study withdrawal) will also be recorded. In addition, events meeting the criteria of a Serious Adverse Event (SAE) must be reported to the Sponsor within 24 hours on the SAE reporting forms.

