10.3.11 Data presentation

10.3.11.1 Demographic and Baseline Characteristics:

Demographic (e.g., age, sex, race, ethnicity) and baseline characteristics (e.g., weight, height) summarized using descriptive statistics, overall and by treatment group for the ITT analysis population.

10.3.11.2 Medical History and Physical Examination:

The number and percent of subjects with past and current medical disorders at the time of enrollment will be presented overall and by treatment group for the ITT analysis population. Results of any abnormalities documented from the physical examination will be summarized overall and by treatment group for the safety and ITT analysis populations.

10.3.11.3 Concomitant Medications or Treatments:

The number and percent of subjects receiving concomitant medications or treatments prior to and during the study and at the final visit will be tabulated and presented overall and by treatment group for the ITT analysis population. Concomitant medications/treatments will be summarized using descriptive statistics and will be presented by type of drug (WHO DRUG classification) overall and by treatment group for the safety and ITT analysis populations.

10.3.11.4 Safety data:

Safety data will be evaluated by changes in vital sign measurements and the frequency and severity of AEs. Concomitant medication will be recorded for safety.

Adverse events:

The Investigator is responsible for monitoring the safety of subjects who have enrolled in the study. All AEs considered to be possibly related to Ampion™ will be followed until the event resolves or stabilized without further change. Subjects will be followed for the occurrence of AEs until completion of the study at Visit 17 or until early termination from the study (if applicable).

Investigators are required to document all AEs occurring during the clinical trial, commencing with the first day of treatment and including the protocol-defined post-treatment follow-up period on the appropriate CRF pages.

The severity of AEs (mild, moderate, severe), relatedness (related, possibly related, unrelated) along with the duration, action taken, and outcome (e.g., study withdrawal) will also be recorded. In addition, events meeting the criteria of a Serious Adverse Event (SAE) must be reported to the Sponsor within 24 hours on the SAE reporting forms.

10.3.11.5 Efficacy data:

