4.8 MISSING DATA

All data collected under this study protocol will be included in the assessment of subject safety. Missing or incomplete AE data will assume greatest relationship to study drug and/or severity.

For the exploratory effectiveness endpoints (WOMAC A, WOMAC C, and PGA), missing values will be imputed when the ITT analysis population is used. The Worst Observation Carried Forward (WOFCF) will be selected as the primary method of imputing missing data. Alternate imputation methods that may be employed will include multiple imputations (SAS PROC MI and SAS PROC MIANALYZE) and Last Observation Carried Forward (LOCF).

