5.2 Definitions

Adverse Event (AE)

An adverse event (AE) is defined as any undesired medical occurrence in a patient or clinical investigation patient receiving a pharmaceutical product and which does not necessarily have a causal relationship with this treatment. An AE can therefore be any unfavorable sign and unintended sign (including an abnormal laboratory finding comparing pre-treatment to post-treatment), symptom, or disease temporarily associated with the use of a study drug, whether or not related to the study drug.

AEs will be graded for severity using the following categories. Missing grade will be assigned a grade of 3 (severe) in tabulations.

Grade 1 (MILD): The symptom is barely noticeable to the study patient and does not influence performance or functioning. Concomitant medication is not ordinarily indicated for relief of mild AEs.

Grade 2 (MODERATE): The symptom is of sufficient severity to make the study patient uncomfortable and to influence performance of daily activities. Concomitant medication may be indicated for relief of moderate AEs.

Grade 3 (SEVERE): The symptom causes severe discomfort, sometimes of such severity that the study patient cannot continue in the study. Daily activities are significantly impaired or prevented by the symptom. Concomitant medication may be indicated for relief of severe AEs.

Relationship to study drug will be codes using the following categories. Missing relatedness will be assigned to “related” in tabulations.

Unrelated: The adverse event is unlikely to have been caused by study drug.

Possibly related: It is unclear whether the adverse event may have been caused by study drug.

Related: The adverse event is likely to have been caused by study drug.

Serious Adverse Event:

A serious adverse event (SAE) is defined as an adverse event that

- Results in death
- Is life-threatening (patient is at immediate risk of death from the event as it occurred)

- Requires in-patient hospitalization (formal admission to a hospital for medical reasons) or prolongation of existing hospitalization
- Results in persistent or significant disability/incapacity
- Results in a congenital anomaly/birth defect

Treatment-Emergent AE:

A treatment-emergent AE (TEAE) is any AE that begins or increases in severity after the initial dose of study drug.

Age

Subject's age is defined as its integer value in years at enrollment.

Baseline

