For any variable, unless otherwise defined, baseline is the last assessment taken prior to the first study drug administration.

Change from Baseline:

The arithmetic difference between a post-baseline value and the baseline value:

Change from Baseline = (Post-baseline Value – Baseline Value)

Percentage Change from Baseline = [(Post-baseline Value – Baseline Value) / Baseline Value] x 100

End of Study

End of study is at Visit 17 (Day 280 ± 14 days), unless terminated early.

Enrollment date

Enrollment date is the same as the randomization date and is designated Day 0.

Study drug

Study drug in this study is Ampion or saline.

Randomization date

Randomization date is the day the subject is assigned a randomization number on study Day 0.

Study Day 0

Day 0 is defined as the first day that study drug is administered to the subject.

Study Day

Day of treatment: study day = (visit date - date of Study Day 0)

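### SAP 4.7.4 ends follow-up for new adverse events at 12 weeks, against its own next paragraph and Visit 17 elsewhere; a smaller point is that the TEAE definition does not name its starting injection

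*SAP*

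**What the plan says.** **End of the AE window.** Under adverse events, SAP 4.7.4 states: "Subjects will be followed for the occurrence of AEs until 12 weeks after the first dose of study medication". The next paragraph requires documentation of all AEs "commencing with the first day of treatment through the end of study", and SAP 5.2 says: "End of study is at Visit 17 (Day 280 ± 14 days), unless terminated early". The SAP schedule (Section 10) marks AEs at every visit from 9 to 17 and at Early Termination. In Protocol 10.3.11.4 the matching sentence has subjects "followed for the occurrence of AEs until completion of the study at Visit 17" or early termination. Protocol 9.3 also closes the reporting period at Visit 17. SAP 4.8 adds: "All data collected under this study protocol will be included in the assessment of subject safety".

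**Start of the TEAE window.** SAP 5.2 defines a TEAE as "any AE that begins or increases in severity after the initial dose of study drug", without naming a study or visit. The same section says: "Study drug in this study is Ampion or saline". The extension gives no saline (SAP 4.6).

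**The concern.** The primary endpoint is the incidence and severity of TEAEs, and the primary objective is safety under repeated injections (SAP 2.1 and 3.1). A 12-week limit from the first extension dose would describe roughly the period after one injection. That is the period before repeat dosing begins.

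The sentence cannot be read as covering events already under way. The sentence before it deals with following related or possibly related events to resolution, so this one concerns new events.

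The start matters less but bears on the same endpoint. Depending on which injection is meant, AEs that began in the main study or in the roll-over gap of up to 170 days are either TEAEs or not. The main study was randomized 6:1 (Protocol 1.2) with a saline arm (SAP 2.4). For some subjects a main-study start would therefore count AEs that began after saline.

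**Working it through.** **Inputs.** Extension injections fall at Visits 9, 11, 13 and 15, nominal Days 0, 84, 168 and 252; Visits 11, 13 and 15 have a ± 14-day window (Protocol 5 and Table 6.1). Visit 17 is Day 280 ± 14, that is Day 266 to 294. The roll-over gap from main-study Visit 7 to Visit 9 is 0 to 170 days (Table 6.1, footnote 1). Assumption: Visit 7 falls on main-study Day 84, because its visit window is not given.

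**The plan's own figure.** Main study plus extension is 12 + 40 = 52 weeks, which reproduces. It is exact only with no gap: 84 + 0 + 280 = 364 days = 52 weeks. With a 170-day gap it is 84 + 170 + 280 = 534 days, or 76.3 weeks.

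**End: share of extension follow-up covered by a 12-week limit**

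- Nominal: 84/280 = 30.0%, leaving 196 days uncovered.
- Visit 17 at its earliest: 84/266 = 31.6%.
- Visit 17 at its latest: 84/294 = 28.6%.
- Second injection: nominally on the day the limit falls. If Visit 11 is at its earliest, 84 − 14 = Day 70, then 84 − 70 = 14 days after it are covered.
- Third and fourth injections: earliest 168 − 14 = Day 154 and 252 − 14 = Day 238, so never covered.
- Counted from the main-study dose instead, the limit falls on main-study Day 84. Visit 9 is then at Day 84 to 254, so no extension follow-up is covered.

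**Start: length of the TEAE window to Visit 17**

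| Starting injection | Shortest | Longest |
|---|---|---|
| Visit 9 (extension) | 266 days | 294 days |
| Main study | 84 + 0 + 266 = 350 days | 84 + 170 + 294 = 548 days |

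For the same Visit 17 day, the ratio of the two windows runs from 378/294 = 1.29 (no gap, latest Visit 17) to 520/266 = 1.95 (170-day gap, earliest Visit 17).

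**Which injection do the documents point to?**

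- Towards Visit 9: SAP 4.2 counts time from the initial dose for this study. SAP 5.2 says "Enrollment date is the same as the randomization date and is designated Day 0". Protocol Table 6.1, footnote 1, makes the first extension injection Day 0.
- Towards the main study: Protocol 9.3 opens AE reporting at the main-study injection. Protocol 10.3.6 counts time on study from the main-study dose. The objective in SAP 2.1 speaks of 52 weeks and five injections, whereas the extension alone gives 40 weeks and four.
- Either way: SAP 5.2 makes Study Day 0 the first day on which the subject receives study drug. With saline included in that term, this can be read as either injection. The safety population (Protocol 10.3.1) settles who is counted, not which dose starts the clock.

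The unnamed injection carries into SAP 9.1, which moves some incomplete AE start dates to an unspecified first dose. At Visit 9 the protocol separates ongoing and new pre-injection AEs from those after the injection (5.1.1; Table 6.1, footnote 7). The SAP text does not say how the pre-injection AEs are tabulated.

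**The case against.** **On the end.** The 12-week sentence describes follow-up and sits among investigator duties; nothing in the SAP turns it into a data filter. The TEAE definition has no end date, SAP 4.8 includes all collected data, and the adjacent paragraph runs to the end of study. A programmer would have to disregard all three to drop later events. This stands. A reader might infer that AEs after week 12 will go uncollected, or will be missing from the primary analysis. The documents support neither inference: collection to Visit 17 is scheduled in both documents, and the 30% describes a literal reading, not an expected result. The objection does not remove the contradiction, which lies in the SAP's own safety section and concerns the primary endpoint.

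**On the start.** SAP 4.2 and the enrollment-date definition already lean to Visit 9. Protocol 9.3 sets a reporting period and 10.3.6 a time origin, and neither defines a TEAE. Under the Visit 9 reading, a pre-injection AE is not treatment-emergent unless it later worsens. The adverse event listing (16.11) has no TEAE restriction in its title, and the outputs themselves are in a separate document. All of that is fair, and it limits confidence in this half. But a lean is not a definition: the objective's 52 weeks and five injections, and the mention of saline, pull the other way. SAP 4.8 cannot decide the matter, since it does not say which AEs are treatment-emergent.

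A reader might also take the 1.29 to 1.95 ratio as the inflation in TEAE incidence. It is a ratio of calendar time only. No scheduled contact is shown between Visit 7 and Visit 9, and the documents give no AE counts for the period before Visit 9.

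**Conclusion.** The contradiction at the end of the window is established with high confidence. SAP 4.7.4 is wrong as written. Taken literally from the first extension dose, it covers 84 of 280 days (28.6% to 31.6% across the Visit 17 window) and almost none of the repeat-dose period. Because every other passage on AE follow-up leads to Visit 17, truncation in practice is unlikely. The weakness is in prespecified tabulation, not in data collection.

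The start of the window is a real but smaller ambiguity, held with moderate confidence. The start is neither wholly undefined nor settled on Visit 9. The two readings give 266 to 294 and 350 to 548 calendar days, on the assumption that main-study Visit 7 falls on Day 84. The effect on TEAE incidence cannot be computed.

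Both should be corrected before the safety tables are programmed. No sample-size figure changes.

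**What to change.** 1. In SAP 4.7.4, replace the 12-week limit with Visit 17 or Early Termination, matching Protocol 10.3.11.4.
2. In SAP 5.2, name the injection that starts the TEAE window, and remove or explain the reference to saline.
3. Use that same injection date as the first dose in the SAP 9.1 imputation table.
4. State whether AEs from the main study and the roll-over gap are tabulated separately from those after Visit 9. If both views are wanted, give two labelled summaries and say which is primary.
5. Reconcile the chosen start with the reporting period in Protocol 9.3 and the time origin in Protocol 10.3.6.

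The cost is SAP wording plus, for item 5, a short protocol clarification. No new data are needed: AEs are already collected at every visit to Visit 17, and Visit 9 already separates events before and after the injection.
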